A Clinical Study Comparing the Basic Performance and Blood Compatibility Characteristics of Nipro ELISIO-H, Gambro Polyflux Revaclear, and Fresenius Optiflux Dialyzers

> [name] MD FRCP (UK) FACP FASN Professor of Medicine (Nephrology) University of Missouri Hospitals and Clinics Columbia MO 65212 And Dialysis Clinic Incorporated Columbia, MO 65201

> > May 5, 2015

Introduction

The dialyzer ELISIO-H is a new high-flux dialyzer made from POLYNEPHRON[™] fiber designed and manufactured by Nipro Corporation Japan. The dialyzer has already been subjected to in-vitro testing, and all legally required biological safety tests have been conducted and certified by an external institute. A number of clinical studies have already been successfully completed for this membrane mainly in Japan and Europe. Nipro ELISIO-H dialyzers are commercially available for several years outside of U.S.A. On 20th December 2013, ELISIO-H dialyzer is 510k-approved for its sales in U.S.A.

Evaluation Objective

The aim of the study is to confirm the safety and clinical effectiveness of the Nipro ELISIO-H by compare the performance characteristics and hemo-compatibility of Nipro ELISIO-H with those of the commercially available dialyzers in U.S.A., Gambro Polyflux Revaclear and Fresenius Optiflux.

Clinical Investigator

[name] University of Missouri Hospitals and Clinics Columbia, MO 65212 [contact] [contact] Email: [contact]

Sponsor

Nipro Medical Corporation [name] [contact] [contact]

Principal Investigator

[name] University of Missouri Hospitals and Clinics Columbia, MO 65212 [contact] [contact] Email: [contact]

Details

a) Membrane and Dialyzer Types

Dialyzer Labelling	Membrane	Dialyzer Manufactur er	UF Coeff. mL/h/mmHg	Surface m²	Sterilization
Nipro ELISIO-H	POLYNEPHRON ™	Nipro, Japan	67.0	1.5	Gamma
Gambro Polyflux Revaclear	PAES	Gambro USA	60.0	1.4	Steam
Fresenius Optiflux	Polysulfone	Fresenius, USA	60.0	1.6	ETO

b) Design:

Study Design: Clinical study according to the US Federal Law that means no necessity of the permission of authorities, but because of blood sampling a vote of an ethics committee should be procured.

c) Patients

Ten (10) stable patients receiving regular dialysis treatment will be chosen for this evaluation. The n of ten was chosen from previous experience with studies of this kind. However with the expectation of a 20% drop out rate a total of twelve patients will be selected from the patient population meeting the inclusion criteria. Standard hemodialysis will be performed with each dialyzer type.

d) Patient Inclusion Criteria

- ESRD patients 18 years or older
- Stable on hemodialysis for more than 3 months
- Stable hemoglobin 11 g/dl or greater, see attached DCI erythropoietin protocol.
- Stable AV fistula vascular access
- Stable anticoagulation and ESA regimen

- No active infection
- Able to sign informed consent and able to participate in the study
- Medically stable

e) Patient Exclusion Criteria

- Participation in another study which may interfere with the planned study
- Active infection
- Medical conditions which may interfere with the study (cardiac, liver disease,
- Hepatitis)
- Female who are pregnant or planning to be pregnant
- Problem with or allergy to anticoagulation
- Patient cannot tolerate Heparin
- Allergy to dialyzer material e.g. polysulfone

f) Withdrawal Criteria

- Patients own decision.
- Relocation, transportation
- Severe mechanical problems with dialyzers e.g. frequent fiber leakages.
- Hypertensive reactions e.g. erythema, edema.
- Non-compliance with therapeutic regimen.
- Change of anticoagulation scheme.
- Other serious problems induced by treatment.
- Any dialysis-related medical problem judged to be sufficiently serious by the principal investigator to necessitate patient withdrawal.

1. Methods

a) Pre-rinsing of Dialyzers

Setting up and preparation of the dialyzers will be performed per the clinic's normal procedure. This involves a pre-rinsing step before the start of dialysis.. The priming solution will not be infused to the patient. Dialysate flow rate is to be initiated at the beginning of the rinsing procedure. All the dialyzers will be pre-rinsed in the same procedure.

b) Heparinization

The usual heparin type and dosage normally used for each individual patient, including the administration regime (bolus injection and continuous infusion), will be maintained

for each patient unless specified otherwise by the investigator/physician during the evaluation. The total amount of heparin given per treatment will be documented.

c) Blood Flow / Dialysate Flow

Hemodialysis: Blood and dialysate flow rates should be between QB= 300 - 500 ml/min and QD= 2 times QB but should follow existing flow rates for the patient, based on clinic procedure. Blood flow and dialysate flow should remain unchanged for all patients for the duration of dialysis and throughout the evaluation. The ultrafiltration rate, appropriate for each patient and treatment will be maintained and recorded. The blood flow will also be determined in the fistula using a Doppler flow device.

d) Dialysis Regime and Number of Applied Dialyzers

Three consecutive treatments will be performed with each dialyzer type. Blood sampling for measurements will be taken as shown in appendix.

e) Performance and Hemocompatibility Parameters to be measured

Please refer to Appendix.

f) Blood Sampling

Blood will be collected pre-, during and post-dialysis at appropriate time intervals (see Appendix) for the evaluation of:

- Clearance of urea, creatinine, phosphate, beta-2-microglobulin, myoglobin at 60 min. Five minutes before the collection the flow rate will be adjusted so that at time of collection, QB= 350 mL/min, QD= 700 mL/min and UF= 0 for all patients. Blood is to be collected from venous side first followed by arterial side.
- 2. **Removal Rate** for urea, creatinine, phosphate, beta-2-m and myoglobin at 0 min and 240 min will be calculated.

3. Hemocompatibility

- (a) Blood cell count (white blood cell and platelet counts).
- (b) Hb / Hct.
- (c) C5a (activation of complement)
- (d) Thrombin-Antithrombin Complex (TAT)

The samples will be collected after confirming that the blood and dialysate flows are at the targeted rates listed above, venous and arterial pressure at point of collection are to be recorded as well. For blood volumes see appendix B.

g) Visual estimation of the amount of clotted capillaries

After dialysis removal of the residual blood is performed by means of ultrafiltration with reverse osmosis water from dialysate compartment to blood compartment (0.5-1 bar water pressure and the overall appearance of dialyzer will be photographed, with focus on the clotted fibers and any residual header blood. This will be carried out at the end of each treatment for each dialyzer (3 times each dialyzer). The number of clotted capillaries in the dialyzer are counted after removal of the plastic casing and classified by the following table.

	Number of clotted fibers							
	0 – 10 11 – 20 21 – 50 51 – 100 >100							
Score	1	2	3	4	5			

2. Data Collection

All data, including blood flow rates, dialysate composition, heparin schedule (i.e. concentration in the pre-rinsing solution, bolus and infusion rates, all medications given to or taken by the patient, and standard dialysis symptom/events seen routinely in dialysis patients will be recorded in the case report form. The patients' records will contain the patients' names, dates of birth, patients' ESRD diagnosis, and duration of treatment on dialysis. Data will be entered into a locked dataset on a locked computer in the Nephrology Research Laboratory. Data will be analyzed in house with the exception of digital analysis of the photos taken of the dialyzers when dialysis is completed which will be done by the sponsor who will be blind to source of the photos. At this time it is not anticipated that any individual data, only aggregate results will be sent to the sponsor but if any individual data is sent to the sponsor will be blinded. All data will be stored by the Division of Nephrology in the Nephrology Research Laboratory for the designated time period and then destroyed.

8. Patient Informed Consent Form

The investigation has the character of a clinical study according to the US requirements and with reference to the European Standard ISO 14155 and the Declaration of Helsinki. All patients must be informed about the aim of the study, the risks, and rights and have to sign a consent form.

9. Confidentiality

The principal investigator and evaluation sponsor accept that all details of the evaluation be kept confidential at all stages of the evaluation. The sponsor also has the right to inspect results prior to any publication or presentation; written consent from the evaluation sponsor is required before the results are published or presented at scientific meetings.

Date: _____

Principal Investigator

Clinical Investigator

Sponsor

A Clinical Study Comparing The Basic Performance and Blood Compatibility Characteristics of Nipro ELISIO-H, Gambro Polyflux Revaclear, and Fresenius Optiflux Artificial Kidneys

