Appendix A: Parameters

Sampling will be done for every dialysis treatment (3 times per dialyzer, per patient)

Performance		60 min	
Clearance	Urea	V, A	
63	Phosphate	V, A	
63	Creatinine	V, A	
"	ß2-m	V, A	
"	Myoglobin	V, A	

ĪĒ

XVenous sampling will be first, followed by the arterial

%Do not adopt "slow flow sampling method".

Performance	pre	240 min
Removal Rate Urea	А	А
" Phosphate	А	А
" Creatinine	А	А
" ß2-m	А	А
" Myoglobin	А	А

Sampling will be done once per patient, per dialyzer

Hemocompatibility	Pre	15 min	30 min	60 min	240 min
WBC	А	А	А	А	А
Platelet Count	А	А	А	А	А
Hb / Hct	А	А	А	А	А
C5a	А	А	А	А	А
ТАТ	А			А	А

A Clinical Study Comparing The Basic Performance and Blood Compatibility Characteristics of Nipro ELISIO-H, Gambro Polyflux Revaclear, and Fresenius Optiflux Artificial Kidneys

	Residual blood behaviour					*)
--	--------------------------	--	--	--	--	----

A: arterial sample (= pre-dialyzer)

V: venous sample (= post-dialyzer)

*) visual evaluation after intensive rinsing

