Statistical Analysis Plan

For

A Clinical Study Comparing the Basic Performance and Blood Compatibility Characteristics of Nipro ELISIO-H, Gambro Polyflux Revaclear and Fresenius Optiflux Dialyzers

NCT02433210

July 23, 2019

Software:

Data were analyzed in house using SigmaPlot for Windows 11.2 (Systat Software, Inc., San Jose, CA, USA) for statistical analysis.

Methods:

Parametric non-paired t-test was used to compare groups except where the data failed the normality test or the variance test, then the nonparametric Mann–Whitney Rank Sum was utilized to test for significance.

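### The aim is to confirm safety and effectiveness, but the SAP specifies only unpaired difference tests with no effect estimate or interval, so a null result could not separate similarity from imprecision

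*Protocol*

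**What the plan says.** The protocol's Evaluation Objective reads: "The aim of the study is to confirm the safety and clinical effectiveness of the Nipro ELISIO-H". This is to be done by comparing performance and hemocompatibility with the "commercially available dialyzers in U.S.A., Gambro Polyflux Revaclear and Fresenius Optiflux".

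Section c) Patients sets the size: "Ten (10) stable patients receiving regular dialysis treatment will be chosen for this evaluation". The basis given is: "The n of ten was chosen from previous experience with studies of this kind". For attrition, "with the expectation of a 20% drop out rate a total of twelve patients will be selected". No effect size, SD, power or margin is stated.

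On design, Methods d) says: "Three consecutive treatments will be performed with each dialyzer type". Appendix A has the performance measures sampled at all three sessions per dialyzer in each patient, and the hemocompatibility measures at one session per dialyzer in each patient. Appendix B totals blood volume per patient over three weeks. The documents do not use the word crossover, but together these indicate that each patient uses all three dialyzers.

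The SAP's whole Methods section is one sentence. Groups are compared by an unpaired t-test; where the normality or variance check fails, a Mann-Whitney rank sum test is "utilized to test for significance". It gives no alpha, sidedness, analysis unit, effect estimate or interval.

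**The concern.** A test of difference can show that two dialyzers differ. It cannot by itself show that they are alike, and an aim worded as confirmation against marketed products invites that reading. With ten patients, a non-significant p-value can arise because the devices perform alike or because the data cannot tell. Without an estimate and its interval, the reader cannot separate the two. What is at stake is how any null comparison with Revaclear or Optiflux is interpreted.

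**Working it through.** **The plan's own figure.** The n of 10 cannot be reproduced, because no alpha, power, effect size, SD or margin is given. Only the dropout step can be checked: 10 × 1.20 = 12, as stated. Dividing instead gives 10 / 0.80 = 12.5, or 13, and 12 × 0.80 = 9.6 expected completers. The gap is small and does not affect this point.

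**Inputs.** n = 10 evaluable or 12 enrolled (section c) Patients); the unpaired t-test (SAP Methods). Assumed, because the documents are silent: two-sided alpha 0.05, one value per patient per dialyzer, a common SD, and the within-patient correlation ρ between dialyzers. SD means the between-patient SD of the value analyzed: a single reading for hemocompatibility, or the three-session mean for performance.

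**Unpaired 95% CI half-width**, t(0.975, 2n−2) × √(2/n), in SD units:
- n = 10: 2.101 × √0.2 = 2.101 × 0.447 = **0.94**
- n = 12: 2.074 × √(2/12) = 2.074 × 0.408 = **0.85**

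On the planned analysis, an observed difference of zero with n = 10 would come with an interval of about ±0.94 SD.

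**Power of the unpaired t-test, n = 10**, treating the groups as independent: 19%, 40% and 56% for true differences of 0.5, 0.8 and 1.0 SD. A true 0.8 SD difference would be non-significant about 60% of the time.

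**Within-patient 95% CI half-width, n = 10**, t(0.975, 9) × √(2(1−ρ)/10), with t = 2.262:

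| Assumed ρ | √(2(1−ρ)/10) | Half-width (SD) |
|---|---|---|
| 0 | 0.447 | 1.01 |
| 0.3 | 0.374 | 0.85 |
| 0.5 | 0.316 | **0.72** |
| 0.7 | 0.245 | **0.55** |
| 0.8 | 0.200 | **0.45** |

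Pairing narrows the interval at each correlation shown from 0.3 upward. At ρ = 0 it is slightly wider than the unpaired one, because of the lost degrees of freedom.

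**Sessions as the unit.** Counting 30 sessions per dialyzer as independent gives t(0.975, 58) × √(2/30) = 0.52, in session-level SDs. That ignores clustering of three sessions within a patient, and it is not available for hemocompatibility, which is sampled at one session per dialyzer.

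**Safety.** If a given event were seen in none of ten patients, the one-sided 95% upper limit on its rate would be 1 − 0.05^(1/10) = 26%. The SAP names no analysis of the symptoms and events recorded on the case report form.

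**The case against.** The strongest reply is that the harm is hypothetical. Neither document says that a non-significant test will count as confirmation. The title says the study compares, the device was already cleared, and *confirm* may be ordinary post-clearance wording. A reader might infer that the plan intends to treat non-significance as success; the documents do not support that. They leave the reading open, and one sentence would close it.

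A reader might also infer that p-values are the only output. That goes too far. The protocol plans clearances, removal rates, cell counts, C5a, TAT and a clotting score, and Data Collection mentions aggregate results. The SAP names tests without limiting what is reported. What stands is narrower: no effect estimate or interval is specified.

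Third, it is tempting to say that large differences remain possible. This is not shown. No SD is given, and Methods f) fixes blood flow, dialysate flow and ultrafiltration at the clearance sample, which should remove some variation. Whether 0.94 SD is large or trivial in mL/min is unknown.

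Fourth, part of the 0.94 SD belongs to the choice of an unpaired test, a related but separate matter. This stands: the within-patient figures show how much narrower the interval could be from the same data.

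**Conclusion.** The concern holds as a mismatch between aim and analysis. The aim is to confirm by comparison, but the specified tests cannot support confirmation from a null result, and nothing in the plan supplies the estimate and interval that would show how informative that result is. It does not follow that the study cannot answer its question at all: a clear difference could still be detected, and the limit applies to null results.

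The 95% CI half-width is 0.94 SD at n = 10 (0.85 SD at n = 12) for the planned unpaired analysis, against 0.72, 0.55 and 0.45 SD for a within-patient analysis of ten patients at correlations of 0.5, 0.7 and 0.8. These figures rest on two-sided alpha 0.05, one value per patient per dialyzer, and correlations that are assumed rather than taken from the documents. They show relative precision only and cannot be expressed in mL/min or percent. The change should be made: it bears on the main conclusion and needs no new data.

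**What to change.** In a dated SAP amendment:

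- For performance outcomes, average the three sessions per patient per dialyzer, so that the patient is the analysis unit.
- Make the main result for each outcome the within-patient difference, ELISIO-H minus each comparator, with its 95% CI in the outcome's own units. State the number of patients contributing to each difference.
- For the ordinal clotting score in Methods g) and for clearly non-normal outcomes, report a paired rank-based or median difference with its interval. Say how repeated scores are reduced to one per patient per dialyzer.
- State that a non-significant test will not be read as equivalence or confirmation.
- Describe the conclusion as estimating and comparing rather than confirming. On that wording no margin is needed.

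The planned sampling already supplies the data, so no patients or blood draws are added. The cost is a weaker claim. Because the SAP is dated July 2019 and written in the past tense, the analysis may already have been done, so the amendment must be disclosed as a late change and the originally specified unpaired results reported alongside.

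### The order of the three dialyzers is not specified, randomised or balanced, so the plan permits dialyzer and week to be confounded; separately, the SAP compares the same patients with a non-paired test

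*Protocol*

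**What the plan says.** Protocol, Methods d): "Three consecutive treatments will be performed with each dialyzer type". Appendix A, on clearance and removal rate: "Sampling will be done for every dialysis treatment (3 times per dialyzer, per patient". Hemocompatibility is sampled in one session per patient per dialyzer. Appendix B lays out a Monday/Wednesday/Friday week and multiplies its blood volume by three weeks per patient. I read this as one dialyzer per week, although the Protocol does not say so in words.

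The Study Design entry gives only the regulatory status. The device table lists the three dialyzers but is not presented as a treatment sequence. I found nothing in either document on order, randomisation of order, balance across patients or washout.

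SAP, Methods: "Parametric non-paired t-test was used to compare groups", with the Mann–Whitney test as fallback when the normality or variance check fails. No patient, period or order term is named.

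Several provisions hold conditions steady. Methods c): "Blood flow and dialysate flow should remain unchanged for all patients for the duration of dialysis and throughout the evaluation". Methods f), for clearance sampling: "QB= 350 mL/min, QD= 700 mL/min and UF= 0 for all patients". The entry criteria include "Stable anticoagulation and ESA regimen" and "Stable hemoglobin 11 g/dl or greater". Usual heparin is maintained unless the physician specifies otherwise, and a change of anticoagulation scheme is a withdrawal criterion.

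**The concern.** The stated objective is to compare dialyzers, and each patient receives them in successive blocks. Anything that changes over about three weeks in a patient, a machine or the laboratory also changes between blocks. If the order differs suitably between patients, such change can be separated from the dialyzer effect. If all patients share one order, it cannot, and more patients do not help.

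The analysis is a second and separate matter. Treating the three sets of values as if they came from different people discards the main advantage of the design, which is that each patient is their own control. Pairing would correct the standard error but would not by itself remove a time trend.

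**Working it through.** **Inputs from the documents.** Three dialyzers; three consecutive sessions each; a target of ten patients, with "with the expectation of a 20% drop out rate a total of twelve patients will be selected". Twelve equals 10 × 1.2. Appendix B adds up: 3 × 28 = 84 ml; 10 + 15 + 22.5 = 47.5 ml; 84 + 47.5 = 131.5 ml/week; × 3 = 394.5 ml. This agrees with three blocks of one week each.

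**Model.** One value per patient per dialyzer, with terms for patient (n columns), period (2) and dialyzer (2), so n + 4 columns. A contrast is estimable if adding it to the design matrix does not raise the rank.

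| Orders used | Patients | Columns | Rank | Dialyzer contrasts estimable |
|---|---|---|---|---|
| One common order | 10 | 14 | 12 | none |
| One common order | 12 | 16 | 14 | none |
| Two orders, 9 of the 15 possible pairs | 10 | 14 | 13 | one of three |
| Two orders, other 6 pairs | 10 | 14 | 14 | all |
| Any three distinct orders | 9 | 13 | 13 | all |
| Six orders, two patients each | 12 | 16 | 16 | all |
| Six orders, after any two dropouts | 10 | 14 | 14 | all |

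The nine deficient pairs are those in which one dialyzer keeps the same week in both orders. Its two contrasts are lost, and the contrast between the other two dialyzers survives.

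**Bias under a common order.** With a drift of d per week and no period term, week-k values carry (k − 1)d. Second minus first is biased by d, third minus second by d, and third minus first by 2d. The number of patients does not enter. With six orders × two patients, the bias from linear drift is 0.

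**Cost of the period term.** Residual degrees of freedom are 36 − 16 = 20 at n=12 and 30 − 14 = 16 at n=10. The contrast variance, in units of the within-patient variance, is 2/12 = 0.167 at n=12 with or without period. After the worst two dropouts it is 0.208 against 2/10 = 0.200, and 0.208/0.200 = 1.04.

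**Non-paired test, no drift and no true difference.** With total variance σ² and within-patient correlation ρ, the difference of two dialyzer means has variance 2σ²(1 − ρ)/n. The non-paired test estimates it as 2σ²/n. The true standard error is therefore √(1 − ρ) times the one used: √0.5 = 0.71 at ρ = 0.5 and √0.2 = 0.45 at ρ = 0.8. By simulation at n=10 and nominal 5%, the t-test rejects 5% of the time at ρ = 0, about 1% at ρ = 0.5 and about 0.1% at ρ = 0.8. The documents give no ρ; these values are assumptions.

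**The case against.** The harm is conditional. A reader might infer that one order was used, perhaps that of the title or device table, and that the comparisons are therefore confounded. The documents do not support this: no list is labelled as a sequence, and an order varied or randomised in practice but not written down cannot be excluded. Nor do they show a time trend or give the size of one, so I attach no false-positive rate to drift. Any such rate would rest on an assumed drift and an assumed correlation.

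The existing controls also count. Clearance is sampled at fixed flows with no ultrafiltration. Removal rate uses samples from within one session, and every hemocompatibility parameter has a pre-dialysis sample. Heparin is maintained and entry requires stable patients. These make a large drift less likely, and that part of the objection stands. They do not replace a balanced order. The clotted-fiber score has no pre-dialysis value, ultrafiltration is set per treatment, and heparin may be altered at the physician's discretion.

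A reader might also infer that the non-paired test inflates false positives. With positive within-patient correlation and no drift, it does the opposite: it is conservative.

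**Conclusion.** The concern holds as a gap in the plan, not as a demonstrated fault in the results. The plan permits a common order. Under one, no dialyzer contrast can be separated from week, and a drift of d per week shifts the estimates by d or 2d at any sample size. This rests on the one-dialyzer-per-week reading of Appendix B; with consecutive blocks of any length, block takes the place of week and the argument is the same. Whether the order was common, and how large d is, cannot be learned from the documents.

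The non-paired test is wrong for these data whatever the order. Its standard error is too large whenever a patient's values are positively correlated, and real differences can be missed. The size of that loss depends on the assumed correlation.

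The change should be made: every between-dialyzer conclusion depends on an order that the plan leaves open.

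**What to change.** 1. If sessions are still to be run, state in Methods d) that the twelve patients are randomised to the six possible dialyzer orders, two per order, and that the order is recorded. The SAP is dated 2019 and written in the past tense, so this step may no longer apply.
2. If the study is complete, tabulate the order that each patient received.
3. Replace the non-paired test with a least-squares model on one value per patient per dialyzer: the mean of three sessions for clearance and removal rate, and the single sampled session for hemocompatibility. Use patient, period and dialyzer terms where the contrasts are estimable. If the order was common, or the orders leave contrasts not estimable, fit patient and dialyzer only and state which dialyzer differences cannot be separated from time.
4. For the ordinal 1–5 clotted-fiber score, use a within-patient rank method, for example Friedman with paired signed-rank comparisons, on one summary value per patient per dialyzer. State that it does not adjust for period.
5. If the SAP's analysis has already been done, label the new one post hoc and report both side by side.

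Cost: a six-order list or a table of orders, and a revised SAP method. The period term takes two degrees of freedom. Under the six-order design it adds nothing to the contrast variance at n=12 and at most about 4% after two dropouts. No extra patients, visits or samples are needed.

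### Clotted fibers are counted, but the plan defines only a banded 1–5 score and never commits to recording or analysing the count; this matters if counts lie mostly below about 10 or above 100

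*Protocol*

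**What the plan says.** Protocol, Methods, item g: after residual blood is rinsed out and the dialyzer photographed, "The number of clotted capillaries in the dialyzer are counted after removal of the plastic casing and classified by the following table". The bands are "0 – 10 11 – 20 21 – 50 51 – 100 >100", scored 1 to 5. On frequency: "This will be carried out at the end of each treatment for each dialyzer (3 times each dialyzer").

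The score is the only clotting result that the protocol defines. Appendix A lists just a visual evaluation of residual blood. Protocol section 2 (Data Collection) sends all data to the case report form, but does not name the fiber count. It also has the sponsor run a blinded digital analysis of the photographs, which is separate from the count.

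The SAP does not mention clotting. Its Methods section gives one rule for every variable: "Parametric non-paired t-test was used to compare groups except where the data failed the normality test or the variance test", with Mann–Whitney as the fallback.

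On size, protocol item c says "Ten (10) stable patients receiving regular dialysis treatment will be chosen for this evaluation" and "The n of ten was chosen from previous experience with studies of this kind". No effect size, SD, alpha or power is given for any measure.

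**The concern.** The effort goes into making a count, yet the only defined result is a coarse grade of it. All counts from 0 to 10 are alike, and so are all counts above 100. If the dialyzers in this trial mostly produce counts at one end, nearly every reading gets the same score, a rank test meets heavy ties, and a t-test has little variation to work with.

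The study aims to compare hemocompatibility, and the clotted-fiber reading is its direct observation of clotting in the device. With ten patients there is little power to spare. A real difference between dialyzers could be reported as no difference simply because the scale cannot show it.

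**Working it through.** **The plan's own figure.** The only computed design figure is the number selected: 10 × 1.20 = 12, as stated. Dividing by the retained fraction gives 10 / 0.80 = 12.5, rounded up to 13. The point here does not depend on this. The n of 10 has no inputs and cannot be re-derived.

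**Step 1: what the bands do to a doubling.** The four closed bands hold 11, 10, 30 and 50 integer values; the fifth is open. Map each count c and its double 2c through the table:

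- Score unchanged: c = 1–5 (2c is at most 10), c = 21–25 (2c is 42–50), and every c above 100. Examples: 4 and 8 both score 1; 22 and 44 both score 3; 110 and 220 both score 5.
- Score always changes: c = 6–20 and c = 26–100.

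So 10 of the 100 starting counts from 1 to 100 hide a doubling, as do all counts above 100. Conversely, one extra fiber (10 to 11, 20 to 21, 50 to 51, 100 to 101) moves the score a full point.

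**Step 2: what that costs in power.** From the protocol: 10 patients, the same patients on each dialyzer, three readings per dialyzer type. Assumed: count = round(m × r × exp(b + e)), with m the median, r = 1 or 2 for the two dialyzers, b (patient) and e (reading) both normal with SD 0.5 on the log scale; two-sided 0.05; 4,000 runs. The analysed value is the mean over readings of log(count+1), or of the score.

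Power, log count v score:

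| Median (v its double) | Paired t, one reading | Paired t, three readings | Unpaired t, three readings |
|---|---|---|---|
| 3 | 77% v 7% | about 100% v 30% | 81% v 27% |
| 15 | 78% v 68% | about 100% v 99% | 83% v 79% |
| 40 | 79% v 67% | about 100% v 99% | 83% v 79% |
| 150 | 79% v 15% | about 100% v 49% | 82% v 39% |

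Hand check of the log-count column. The effect is ln 2 = 0.693. The standard error of the mean paired difference is √(2 × 0.25 / 10) = 0.224 with one reading and √(2 × 0.25 / 3 / 10) = 0.129 with three. The ratios are 3.10 and 5.37, in line with the simulated power. The unpaired test instead divides by about √(2 × (0.25 + 0.25/3) / 10) = 0.258, hence its lower power.

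**Step 3: the SAP's fallback test and other spreads.** Mann–Whitney with 10 independent values per group, 3,000 runs, raw count v score:

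| Medians | log SD 0.5 | log SD 0.8 | log SD 1.2 |
|---|---|---|---|
| 3 v 6 | 80% v 3% | 40% v 12% | 20% v 13% |
| 15 v 30 | 80% v 73% | 41% v 39% | 20% v 19% |
| 150 v 300 | 79% v 13% | 40% v 18% | 20% v 14% |
| 250 v 500 | 81% v about 0% | 40% v 2% | 21% v 8% |

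This ignores the pairing, so it shows relative loss only. The pattern is the same: small in the middle, large at the ends, and weaker as the spread grows.

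**Step 4: is the count alone enough?** With an unpaired t-test and one reading, the untransformed count does worse than the score in the mid-range. At log SD 0.5 it is 46% v 51% at median 15 and 45% v 50% at median 40; at log SD 0.8 it is 11–12% v 18–19%. The mid-range advantage of the count comes from the log scale.

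**The case against.** A reader might infer that the plan throws the count away. The documents do not say so. Item g has fibers counted and classified, and section 2 sends all data to the form; the count is neither named nor excluded. Nor does the SAP assign a t-test to the score: "Parametric non-paired t-test was used to compare groups" is a blanket rule, and clotting is not mentioned. These objections stand. What is supported is the absence of a commitment to record or analyse the count.

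A reader might also infer that the score loses most of its power in general, or that unequal bands are in themselves a defect. Neither holds. The widening upper bands act as a crude ratio scale, and at medians of 15 to 40 with three readings the loss under the Step 2 assumptions is about 1 point paired and about 4 points unpaired. Single-reading figures make the harm look larger than it is under item g's three readings.

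It is also fair that clotting is one measure beside WBC, platelets, Hb/Hct, C5a and TAT, that none is named primary, that the photographs provide a second source, and that a doubling from 3 to 6 fibers is not shown to matter. Using an unpaired test on same-patient data is a separate issue. The step from 81–83% to about 100% on log count comes from pairing and should not be credited to the count.

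What remains is the floor and the ceiling. With no expected counts in the documents, neither can be ruled out.

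**Conclusion.** The point holds in a limited form. The plan has a count made, defines only the 1–5 score as the result, and leaves open whether the count is kept or analysed. That some doublings cannot be seen on the score is plain arithmetic from the table and needs no assumption.

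The power cost does rest on assumptions: log-normal counts, the chosen SDs and a true doubling. On those, with three readings, the score falls to 30% (median 3) or 49% (median 150) against about 100% for log count in a paired test, and to 27% or 39% against 81% or 82% in an unpaired one. In the mid-range it costs little. The loss is therefore material only if counts cluster below about 10 or above 100, and how likely that is cannot be judged from the documents.

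This is a minor point, but more than a missing detail, because a better analysis of a measurement already made is available at almost no cost.

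**What to change.** - Add one case report form field for the actual number of clotted fibers, per treatment.
- Add one SAP sentence: the analysed clotting variable is the within-patient difference between dialyzers in log(count+1), averaged over the three sessions, with the signed-rank test as a check. The +1 allows for zero counts. The log or rank scale is essential; an untransformed count in a t-test would be a step back in the mid-range.
- Keep the 1–5 score as a descriptive summary.

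The cost is that field, that sentence, and slightly longer counting when more than 100 fibers are clotted. The SAP is written in the past tense, so collection may be complete. If the counts were kept, the analysis can still be done, labelled as added later. If only scores were kept, the report should show how many readings scored 1 and how many scored 5, and state the floor and ceiling as a limitation on any finding of no difference.
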